##### 2. Intervention and Control

FICare nursing method guided by Swanson's caring theory encompasses the following five dimensions:

Understanding: A neonatologist provided a comprehensive explanation regarding the developmental progress of premature infants, potential complications, and essential aspects of nursing care to ensure the family gained a thorough understanding

of the care requirements for premature infants.

Accompaniment: Two nursing guides provided essential support to parents of newborns in the NICU, helping to alleviate the anxiety and sense of helplessness among family members and fostering a relationship of trust between the medical staff and the families.

Help: A neonatal nurse played a guiding role in facilitating parental involvement in the daily care of premature infants, which encompassed feeding guidance, introduction of complementary foods, skin care, and related aspects.

Empowerment: A psychological counselor was assigned to provide psychological counseling and guidance to new parents, offering appropriate emotional support and assisting them in accessing necessary social and professional resources.

Maintaining Confidence: A neonatologist and a nurse monitored neonatal development through outpatient visits and telephone follow-ups to encourage families to sustain their confidence in improving infant health outcomes and to support them in maintaining a positive outlook when facing challenges in caregiving.

The control group will continue to receive the traditional model of hospital care, encompassing standard medical services such as physical health monitoring and nutritional support.

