### **Research Plan, Technical Approach, Organizational Structure**

#### **4.1 Research Plan**

##### 1. Inclusion and exclusion criteria

The inclusion criteria were as follows: gestational age ranging from 28 to 36 weeks, stable vital signs for at least 24 hours, and parental accompaniment of preterm infants during hospitalization. The exclusion criteria included: preterm infants with severe congenital or genetic disorders, dysfunction of vital organs, or requiring mechanical life support; preterm infants requiring surgical intervention; and preterm infants with a birth weight below 500 grams.

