### 3. Outcome

The primary outcomes included the corrected head circumference, weight, and height of the newborns at 1 month, 3 months, and 6 months of age. Additionally, parental anxiety and depression status was assessed using the Trait Anxiety Inventory (T-AI), which measures long-term and stable anxiety tendencies, and the State Anxiety Inventory (S-AI), which evaluates current or recent anxiety states. Parental self-efficacy and satisfaction with their parenting role were assessed using the Child-Parental Self-Competence Scale (C-PSOC).

Secondary outcomes included the length of hospital stay, discharge weight, and the number of unplanned hospitalizations.

Confounding factors included fetal gender, gestational age, birth weight, duration of oxygen therapy, duration of total enteral feeding, and the duration required to

transition from full enteral feeding to full oral feeding, defined as the time from the initiation of oral feeding (when preterm infants begin to suck voluntarily and consume the first milk volume exceeding 5 mL) to the complete establishment of full oral feeding.

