#### 5. Statistical Analysis

Measurement data that conformed to a normal distribution were expressed as mean  $\pm$  standard deviation (SD). Independent sample t-tests and paired sample t-tests were employed to assess intergroup statistical differences. For measurement data that did not conform to a normal distribution, results were summarized as median (interquartile range), and the Mann-Whitney U test was applied to evaluate statistical differences between groups. Categorical data were presented as frequency and percentage [n (%)] and analyzed using the chi-square test. Repeated measurement data were examined using repeated measures analysis of variance (ANOVA). All statistical analyses were conducted using SPSS version 25.0.

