#### 4.2 Technical Approach

#### 4.3 Organizational mode

The project leader assumes responsibility for the planning, coordination, and supervision of the entire research process, including decision-making, resource allocation, and risk management. The research focuses on preterm infants, and the project leader is tasked with applying for research sites and securing necessary equipment support. Additionally, the leader collaborates with relevant departments and institutions to promote the implementation of family-participatory care based on Swanson's Caring Theory in the context of preterm infant care. Other project members are assigned specific responsibilities, such as data collection, care

intervention, and outcome analysis. Furthermore, the project's progress and outcomes are regularly evaluated and monitored. Based on these evaluations, the research plan and intervention strategies are adjusted in a timely manner to ensure the study's effectiveness and feasibility.

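### The available text gives no method for assigning families to the two care groups, and the group tests are unadjusted despite listed confounders, so the comparisons are exposed to selection bias of unknown size and direction

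*Combined protocol and SAP*

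**What the plan says.** Section 4.1 (Research Plan) has five consecutively numbered items: eligibility, intervention and control, outcome, sample size, and statistical analysis.

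- **Item 1** sets entry by gestational age, "stable vital signs for at least 24 hours, and parental accompaniment of preterm infants during hospitalization", and lists exclusions.
- **Item 2** describes the five dimensions of the family-participatory care, for example "Two nursing guides provided essential support to parents of newborns in the NICU", and then says "The control group will continue to receive the traditional model of hospital care". It does not say how a family is placed in either group.
- **Item 3** states "Confounding factors included fetal gender, gestational age, birth weight, duration of oxygen therapy, duration of total enteral feeding" and goes on to the time needed to reach full oral feeding.
- **Item 5** states "Independent sample t-tests and paired sample t-tests were employed to assess intergroup statistical differences". For non-normal data, "the Mann-Whitney U test was applied to evaluate statistical differences between groups". It adds chi-square tests and repeated measures ANOVA. No covariate is named for any of these.

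Section 4.2 (Technical Approach) has a heading with no text beneath it. Section 4.3 says "Other project members are assigned specific responsibilities, such as data collection, care" intervention and outcome analysis. It gives nobody responsibility for allocation.

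**The concern.** A comparison of two groups can be protected against selection by assigning at random, with the next assignment hidden from whoever enrols, or (less completely) by adjusting for known prognostic differences. The available text documents neither.

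The gap matters more here for three reasons. Entry leaves some room for judgement about when vital signs count as stable. The intervention cannot realistically be hidden from staff or parents, so an enroller who controls or foresees the assignment could act on it. Several primary outcomes are parental anxiety and parenting-competence scores, which depend directly on which families enter which group. If calmer families or more mature infants went more often to one group, outcomes could differ with no effect of care, and the planned tests could not tell the two explanations apart.

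**Working it through.** **Inputs.** From item 4 of section 4.1: two-sided alpha 0.05 (z = 1.96), power 80% (z = 0.84), variance 2.5, detectable difference d = 1.5, and 18 per group. The documents give no figure for a selection effect, so its size is assumed and shown as a range.

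**Step 1: the plan's own figure.** n = 2 × (1.96 + 0.84)² × 2.5 / 1.5² = 17.42, rounded up to 18 per group. The stated figure reproduces and does not depend on this point.

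**Step 2: what the text provides.**

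| Protection | Where it would be expected | What is there |
|---|---|---|
| Assignment rule (random, or by ward, date or preference) | 4.1, between items 1 and 2 | Nothing |
| Sequence, list holder, concealment | 4.1 or 4.3 | Nothing |
| Adjustment for prognostic factors | 4.1, item 5 | No covariates named |
| Prognostic factors recognised | 4.1, item 3 | Sex, gestational age, birth weight, oxygen and feeding durations |

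**Step 3: what an imbalance would do.** SD = √2.5 = 1.58. Suppose there is no true effect, but the groups differ systematically in prognosis by s SD. The two-sample t statistic with 18 per group then follows a noncentral t distribution with 18 + 18 − 2 = 34 degrees of freedom and noncentrality s × √(18/2) = 3s. The two-sided rejection rates are:

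| Assumed shift s (SD) | Outcome units (s × 1.58) | Share of d = 1.5 | Noncentrality | False-positive rate |
|---|---|---|---|---|
| 0 | 0 | 0% | 0 | 5.0% |
| 0.1 | 0.16 | 11% | 0.30 | 6.0% |
| 0.25 | 0.40 | 26% | 0.75 | 11.3% |
| 0.5 | 0.79 | 53% | 1.50 | 30.8% |
| 0.75 | 1.19 | 79% | 2.25 | 58.9% |

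**Step 4: would more patients help?** No. With 50 per group, a shift of 0.25 SD gives 23.6% and 0.5 SD gives 69.7%. A systematic difference does not average out as numbers grow.

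**Step 5: which listed factors can be adjusted for.** Sex, gestational age and birth weight are fixed before assignment. Oxygen and feeding durations may arise after it and could be affected by the care itself, so adjusting for them could remove part of a real effect.

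**The case against.** The strongest objection is that silence in the available text does not prove the plan lacks an allocation step. The opening pages were not available, and a figure may belong under the empty 4.2 heading; either could say that families are randomised. This stands, and it limits the point to what the available text states. It does not remove it: a label in a title or diagram would be unlikely to give the sequence, its holder and the concealment, and item 5 would still name no adjustment.

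A reader might go further and infer that the study is not randomised, or that its results will be biased. The documents support neither. The list of confounding factors might be read as a sign that chance was not relied on, but it fits a baseline table equally well, and it includes durations that may follow assignment. Some routes for selection are also narrowed: parental accompaniment is required of every infant, and growth is described as corrected, which may deal with part of a maturity difference. Differences in parental anxiety or motivation are not narrowed in this way.

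It is also fair to object that the error rates in the working are generic. They hold for any t-test of this size under a shift of that size, the shifts are assumed, 18 is stated as a minimum, and the variance and d are not tied to a named outcome. The rates show sensitivity and do not measure a known defect. That the study is open is likewise an inference from the nature of the care, since masking is not mentioned.

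**Conclusion.** The point holds in a limited form. The available text states no method of assignment and plans unadjusted comparisons although it names pre-assignment confounders. Followed as written, the comparisons are exposed to selection bias; its presence, direction and size cannot be derived from the documents. For scale only, an assumed shift of 0.25 or 0.5 SD at 18 per group would raise the 5% error rate to about 11% or 31%. The stronger statement, that the trial cannot support a causal conclusion, would follow only if assignment was in fact not random, and the documents do not settle that. The conclusion rests on the available text being the full operational description, apart from the possible content of 4.2 and the opening pages.

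**What to change.** 1. **If enrolment is still open**, add an allocation step between items 1 and 2 of section 4.1. Generate a 1:1 computer sequence by family, with varied block sizes not disclosed to recruiting staff. Have it held by an existing project member who does not recruit, give care, assess outcomes or analyse data. Release it for one family at a time, only after eligibility, consent and baseline data are recorded. The verb tenses in section 4.1 are mixed, so the sponsor should first state whether enrolment has finished. If allocation is already described under 4.2 or in the opening pages, carry these details into 4.1.
2. **In either case**, make the main group comparison a regression or ANCOVA adjusted for sex, gestational age and birth weight, which the plan already collects. Leave out the oxygen and feeding durations.
3. **If assignment was not random**, state how it was done, call the study non-randomised, and limit the conclusion to an association adjusted for those three factors. Adjustment will not remove differences in factors that are not included, such as parental motivation.

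**Cost.** One or two protocol paragraphs and a generated list; the calculated 18 per group does not change. The downsides are a short wait for each assignment, possible contamination between families cared for in the same unit, and a few degrees of freedom (three covariates take the residual from 34 to 34 − 3 = 31). Item 3 schedules no baseline parental measurement, so if one is wanted before release it is an added procedure. If the study was not randomised, the further cost is a more modest conclusion.

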### 3. Outcome

The primary outcomes included the corrected head circumference, weight, and height of the newborns at 1 month, 3 months, and 6 months of age. Additionally, parental anxiety and depression status was assessed using the Trait Anxiety Inventory (T-AI), which measures long-term and stable anxiety tendencies, and the State Anxiety Inventory (S-AI), which evaluates current or recent anxiety states. Parental self-efficacy and satisfaction with their parenting role were assessed using the Child-Parental Self-Competence Scale (C-PSOC).

Secondary outcomes included the length of hospital stay, discharge weight, and the number of unplanned hospitalizations.

Confounding factors included fetal gender, gestational age, birth weight, duration of oxygen therapy, duration of total enteral feeding, and the duration required to

transition from full enteral feeding to full oral feeding, defined as the time from the initiation of oral feeding (when preterm infants begin to suck voluntarily and consume the first milk volume exceeding 5 mL) to the complete establishment of full oral feeding.

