#### 4. Sample Size Calculation

With the assistance of Select Statistical Services (<https://select-statistics.co.uk/calculators/sample-size-calculator-two-means/>), the sample size was determined. This calculation utilizes the following formula to compute the sample size  $n$ :

[figure not shown]
$$n = \frac{2 \times (Z_{\alpha/2} + Z_{\beta})^2 \times \sigma^2}{d^2}$$

Among them, " $Z_{\alpha/2}$ " denotes the critical value of the standard normal distribution at  $\alpha/2$  (for a 95% confidence level,  $\alpha = 0.05$ , and the corresponding critical value is 1.96); " $Z_{\beta}$ " denotes the critical value of the standard normal distribution at  $\beta$  (for a statistical power of 80%,  $\beta = 0.2$ , and the corresponding critical value is 0.84); " $\sigma^2$ " represents the population variance, which is set at 2.5; and "d" refers to the minimum detectable difference, which is set at 1.5 for the primary outcome analysis. Based on these parameters, the required minimum sample size per group is calculated to be 18 participants.

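### Nine growth results are all primary with no success rule, testing order or multiplicity control, and the 80% power is shown for one unnamed comparison only

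*Combined protocol and SAP*

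**What the plan says.** Under 4.1 Research Plan, item 3 (Outcome) says: "The primary outcomes included the corrected head circumference, weight, and height of the newborns at 1 month, 3 months, and 6 months of age". The same paragraph goes on: "Additionally, parental anxiety and depression status was assessed using the Trait Anxiety Inventory (T-AI", followed by the S-AI and the C-PSOC. These three parental scales have no assessment time. They come after the growth outcomes and are not in the secondary list, which reads: "Secondary outcomes included the length of hospital stay, discharge weight, and the number of unplanned hospitalizations".

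Item 4 (Sample Size Calculation) makes one calculation, at alpha 0.05 and 80% power. For the variance it says that the symbol "represents the population variance, which is set at 2.5", and for the difference that d "refers to the minimum detectable difference, which is set at 1.5 for the primary outcome analysis". It gives no measure, age or unit. It concludes: "Based on these parameters, the required minimum sample size per group is calculated to be 18 participants".

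Item 5 (Statistical Analysis) says: "Independent sample t-tests and paired sample t-tests were employed to assess intergroup statistical differences". It also says: "Repeated measurement data were examined using repeated measures analysis of variance (ANOVA"). It assigns no method to a primary outcome, and it does not say whether the group or the group-by-time effect of the ANOVA decides.

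**The concern.** A reader cannot tell which result would make the trial positive. The candidates are three growth measures, three ages, two ANOVA effects and possibly three parental scales. Without a rule, the deciding result can be picked after the data are seen. If one unadjusted significant result is enough, the chance of a false claim exceeds the 5% that the sample size section implies.

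The power statement has a related gap. One difference of 1.5 with variance 2.5 cannot be assumed to suit both a weight and two lengths. As written, the 80% therefore cannot be attached to any stated outcome, nor to any rule that combines several.

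**Working it through.** **Inputs from the plan.** Two-sided alpha 0.05 (z = 1.96), power 80% (z = 0.84), variance 2.5, difference 1.5, 18 per group (item 4); three measures at three ages (item 3).

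**Assumptions, because the documents give no figures.** Exchangeable correlations, ranged from 0 or 0.5 up to 0.9. For joint power, 2.5 and 1.5 are taken to apply at every visit and for every measure.

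**1. The plan's own figure.** n = 2 × (1.96 + 0.84)² × 2.5 / 1.5² = 17.42, rounded up to 18. It reproduces. The standardised difference is 1.5/√2.5 = 0.949. Power at 18 per group for one comparison is 81% by the plan's normal formula and 79% by the noncentral t. The gap between the two is not a fault.

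**2. Family-wise error if any unadjusted p<0.05 counts.** Under independence, error = 1 − 0.95^k. Correlated cases were simulated with t-tests at 18 per group.

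| Tests | Independent | r = 0.5 | r = 0.9 |
|---|---|---|---|
| 3 (one ANOVA group test per measure) | 14.3% | about 13% | about 8.5% |
| 9 (visit-wise t-tests) | 37.0% | about 27% | about 13% |

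If the group-by-time effect of each ANOVA could also count, there are six tests: 1 − 0.95⁶ = 26% under independence. If each parental scale is added once to the nine t-tests, there are twelve: 1 − 0.95¹² = 46% under independence.

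**3. Power at 18 per group, nine visit-wise t-tests.**
- Bonferroni (0.05/9): 47% per test.
- All nine must succeed at 0.05: 0.790⁹ = 12% under independence, 38% at r = 0.5 and 63% at r = 0.9.

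**4. Power at 18 per group, three ANOVA group tests.** With equal variances and exchangeable correlation, the group test is a t-test on the infant's mean over three visits. Its variance is 2.5 × (1 + 2ρ)/3, where ρ is the between-visit correlation.

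| ρ | Variance of mean | Effect (SD) | Power at 0.05 | Power at 0.05/3 | All three at 0.05 |
|---|---|---|---|---|---|
| 0.5 | 1.67 | 1.162 | 92% | 83% | 79-88% |
| 0.7 | 2.00 | 1.061 | 87% | 74% | 66-81% |
| 0.9 | 2.33 | 0.982 | 82% | 67% | 54-74% |

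The last column runs over between-measure correlation 0 to 0.9; its lower ends are 0.923³, 0.871³ and 0.816³. Power at 0.05/3 falls below 80% once ρ exceeds about 0.56. These figures cover the group effect only. Power for group-by-time cannot be derived from a single difference of 1.5.

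**The case against.** The strongest reply is that item 5 already sends repeated measurements to repeated measures ANOVA, so the natural count is three tests, not nine. That is right, and the three-test figures are the ones to lead with. It does not close the gap. Three any-win tests still give 8-14%, the deciding ANOVA effect is not named, and the t-tests in the same section remain available for each visit.

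A second reply is that co-primaries need no adjustment if all must succeed. This is true for the error rate, but the plan states no such rule, and its power under that rule is not shown.

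Three stronger readings are tempting, and the documents do not support them:
- **The 80% power fails for more than one comparison.** Under the stated assumptions, each ANOVA group test has 82-92% unadjusted power, and 83% after Bonferroni at between-visit correlation 0.5. The plan fails to demonstrate power for a joint rule; it does not follow that power is lost.
- **The false-positive risk is 37%.** That needs nine visit-wise tests, an any-win rule and independence. Independence is implausible for the same infants measured repeatedly, and the plan states no any-win rule.
- **The sample size arithmetic is wrong.** It is correct for one comparison with the stated inputs.

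It also stands that the joint-power figures are illustrations. They put a 0.949 SD effect on every measure and age, which nothing in the plan supports.

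**Conclusion.** The concern holds, and it should be settled before the trial's main conclusion is drawn. The plan has several primary results, one unnamed sizing comparison, and no rule linking them.

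The inflation is conditional on any unadjusted significant result counting as success. Given that, error exceeds 5% at every correlation examined, on both the three-test and the nine-test reading, and it is higher still if group-by-time effects or parental scales also count.

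The power conclusion is narrower. The 80% is shown only for a single comparison to which 2.5 and 1.5 apply. With nine visit-wise t-tests, a Bonferroni split or an all-must-succeed rule takes power well below 80%. With three ANOVA group tests, power may stay above 80% or fall below it, depending on between-visit and between-measure correlations that the documents do not give.

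**What to change.** - **Primary test.** Name one primary growth measure and one primary test at two-sided 0.05. This can be one visit by independent t-test, which matches the formula in item 4, or one repeated measures ANOVA with the deciding effect (group or group-by-time) stated.
- **Everything else.** Make the other growth results and the three parental scales secondary, with assessment times for the scales. Alternatively, test further primaries in a stated fixed order at 0.05, stopping at the first non-significant result.
- **Inputs.** State the outcome and unit to which 2.5 and 1.5 belong, and limit the 80% power sentence to that test. If they do not belong to the named outcome, restate the inputs and the resulting power or sample size.
- **Timing.** State when the choice was made relative to seeing outcome data. The outcome and analysis sections are in the past tense, while the control group is described in the future tense. A choice made after the data were seen would not remove the selection risk.

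**Cost.** The changes are to wording in items 3, 4 and 5. No infants are added for one primary, or for the first test in a fixed order, if 2.5 and 1.5 belong to that outcome and the test is the one-visit t-test or the ANOVA group effect. A group-by-time primary needs its own power calculation. The price is that most current primaries become supportive or sit lower in the order with less power, and the power claim narrows.

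A Bonferroni route could need more infants. Under the assumptions above, 80% power per test takes 31 analysed per group for nine visit-wise t-tests, or 18, 21 and 24 for three ANOVA group tests at between-visit correlation 0.5, 0.7 and 0.9.

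### The primary growth outcome does not say whether age counts from birth or from term, and the planned group comparison adjusts for neither age nor sex

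*Combined protocol and SAP*

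**What the plan says.** Under 4.1 Research Plan, item 3 (Outcome), the growth part of the primary outcome reads: "The primary outcomes included the corrected head circumference, weight, and height of the newborns at 1 month, 3 months, and 6 months of age". The word *corrected* stands before the measurements, and the visits are set in months of age. Nowhere does the text use the term corrected age, give the origin from which age is counted, define a correction, name a growth reference or set a visit window.

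Item 1 (Inclusion and exclusion criteria) admits infants with "gestational age ranging from 28 to 36 weeks".

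The Outcome section also states: "Confounding factors included fetal gender, gestational age, birth weight, duration of oxygen therapy", followed by feeding durations. It does not say how these factors enter the analysis.

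Item 5 (Statistical Analysis) states: "Independent sample t-tests and paired sample t-tests were employed to assess intergroup statistical differences". It adds the Mann-Whitney U test, the chi-square test and, for repeated measurements, repeated measures ANOVA. It names no covariate and no standardisation for age or sex.

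**The concern.** In preterm infants, what *months of age* means depends on the origin. Counted from birth, a visit finds infants at different stages of maturity. Counted from term, it finds them at the same stage. The sentence can be read either way, so two competent teams could follow this plan and collect different primary data.

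The analysis does not close the gap. The authors recognise that sex and gestational age matter, since they list both as confounders, but the named tests use neither. Even if visits are tied to corrected age, differences in sex and in the actual day of measurement stay in the comparison. If visits are tied to birth, the spread in gestational age at entry is added to them.

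At stake is the precision of the primary growth comparison and, if the groups differ in gestational age, its validity.

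**Working it through.** **The plan's own figure.** The Sample Size Calculation uses Z = 1.96 and 0.84, variance 2.5 and minimum difference 1.5:

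n = 2 × (1.96 + 0.84)² × 2.5 / 1.5² = 17.42, rounded up to 18 per group.

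The stated 18 reproduces. The variance and the difference carry no unit and are not tied to a named outcome, so they cannot be compared with the weight figures below. The 2.5 may already include spread from maturity.

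**Inputs from the documents.** Gestational age 28 to 36 weeks; visits at 1, 3 and 6 months; 18 per group.

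**Inputs assumed (not in the documents).** Weight gain 0.15 to 0.25 kg per week around the 1-month visit. SD of weight among infants of the same maturity 0.4 to 0.5 kg. SD of gestational age 1.5 weeks (clustered) to 2.58 weeks (whole weeks 28 to 36 equally frequent: √((9² − 1)/12) = 2.58).

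**Step 1. Maturity at each visit if age counts from birth.** Postmenstrual age = gestational age + months × 30.44/7.

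| Visit | Born at 28 weeks | Born at 36 weeks |
|---|---|---|
| 1 month | 32.3 weeks | 40.3 weeks |
| 3 months | 41.0 weeks | 49.0 weeks |
| 6 months | 54.1 weeks | 62.1 weeks |

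The gap is 36 − 28 = 8 weeks at every visit. If 36 means up to 36 weeks and 6 days, it is almost 8.9 weeks. If age counts from 40 weeks, the gap from this source is 0.

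**Step 2. How far the two readings move a visit.** 40 − 28 = 12 weeks for the least mature infant; 40 − 36 = 4 weeks for the most mature.

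**Step 3. Share of variance in 1-month weight due to maturity, birth-date reading only.** Share = (g × s)² / [(g × s)² + w²], with g the weekly gain, s the SD of gestational age and w the same-maturity SD.

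| s (weeks) | g (kg/week) | w (kg) | g × s (kg) | Share |
|---|---|---|---|---|
| 1.5 | 0.15 | 0.5 | 0.225 | 17% |
| 1.5 | 0.25 | 0.4 | 0.375 | 47% |
| 2.58 | 0.15 | 0.5 | 0.39 | 37.5% |
| 2.58 | 0.25 | 0.4 | 0.65 | 72% |

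**Step 4. Chance imbalance between groups, same reading.** Even with random allocation, the standard error of the difference in mean gestational age at 18 per group is s × √(2/18): 0.50 weeks for s = 1.5 and 0.86 weeks for s = 2.58. Multiplied by 0.15 and 0.25 kg per week respectively, that is about 0.08 to 0.22 kg.

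**Step 5. What remains under corrected age.** Sex differences and visit timing remain. At the same assumed rates, a visit one week late shifts weight by 0.15 to 0.25 kg.

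**The case against.** The strongest reply is that *corrected* is simply misplaced, perhaps in translation, and that the authors mean 1, 3 and 6 months corrected age. In a sentence about preterm infants that is the natural reading, and booking visits by birth date means ignoring the word. This stands: the 8-week gap and the variance shares apply only if the less likely reading is put into practice.

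Several stronger inferences are tempting and are not supported:

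- *The trial measures infants by birth date.* The text leaves the origin open; it does not fix it at birth.
- *A measurement cannot be corrected, so the sentence is meaningless.* A value standardised for age and sex is a corrected measurement. The fault is that no such correction is defined.
- *The outcome is stated in raw units.* No units are given for it. That raw values will be compared is inferred from the absence of any standardisation.
- *The groups differ by 8 weeks.* Eight weeks is the largest gap between two infants. Both groups share the entry criteria, so the main effect is added variance.
- *The two arms will read the sentence differently.* Nothing in the documents suggests this.

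The plan also deserves credit for listing sex and gestational age as confounders. But a list without a method changes nothing in the t-tests or the ANOVA. Nor can balance on gestational age be presumed, since the readable text describes no allocation method. (Section 4.2, Technical Approach, has no text under its heading, and a figure may be missing there.)

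**Conclusion.** The concern holds as an undefined age scale for a primary outcome, together with an analysis that leaves out age and sex although the plan names sex and gestational age as confounders. It does not show that the trial used birth-date visits, that the comparison is biased or that the sample size arithmetic is wrong.

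Its size depends on the reading. Under corrected age, the maturity gap disappears and what remains is uncontrolled variation in sex and exact visit day. Under birth-date visits, infants differ by up to 8 weeks, and maturity accounts for roughly 17% to 72% of the variance in 1-month weight. That range rests on assumed weekly gain, same-maturity SD and gestational-age spread; only the 28-to-36-week limits come from the plan. The shares were worked out for 1-month weight alone and should not be carried over to head circumference, length or the later visits. Bias, as opposed to noise, follows only if gestational age is imbalanced between the groups.

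The plan should be changed, because the outcome is primary and the remedy is cheap and improves the comparison under either reading.

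**What to change.** 1. Restate the growth outcome as head circumference, weight and length at 1, 3 and 6 months corrected age, counted from 40 weeks postmenstrual age, with one visit window for both arms.
2. Compare the groups on z-scores for sex and exact corrected age on the day of measurement, from one growth standard named in advance. Adjusting raw values for sex, gestational age and exact age at measurement serves the same purpose. Choose one before the data are seen.
3. Report the raw values descriptively.

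**Cost.** Sex and gestational age are already listed in the plan, so only the date of each measurement has to be recorded as well. If corrected age was always intended, the visit change is wording only. If birth-date visits were intended, follow-up ends 4 weeks later for an infant born at 36 weeks and 12 weeks later for one born at 28 weeks. If z-scores become the primary scale, the difference of 1.5 and variance of 2.5 in the Sample Size Calculation must be restated on that scale and the sample size recomputed.
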